8.2 SECONDARY OBJECTIVES

- i) To describe the characteristics of women exposed to CYD-TDV during pregnancy or up to 30 days before the LMP.
- ii) To describe the characteristics of CYD-TDV pregnancy exposure with regards to the number of doses (during pregnancy and overall), dose intervals, trimester of exposure.

9 RESEARCH METHODS

9.1 STUDY DESIGN

9.1.1 Overview

This will be a Pregnancy Registry Study that utilizes active identification and enrollment of a cohort of pregnant women of any age and their offspring who were inadvertently exposed to CYD-TDV anytime during the pregnancy or in the 30 days preceding their LMP (i.e., periconceptional period). The study data collection period will be from July 2016 (first availability of Paraná's Immunization Registry and of CYD-TDV through the private market) to July 2022 (end of last follow up interview for offsprings), and participant enrollment will be from July/August 2019* to July 2020. As such, study outcomes will be retrospective if occurring between July 2016 and the start of participant enrollment, and prospective for outcomes occurring between the start of participant enrollment and July 2022. Data collection will utilize a hybrid approach comprised of the use of structured interviews supplemented by medical records review (primary data sources), and the use of health and mortality

databases (secondary data sources). Study participation will require receipt of a signed informed consent form (ICF) or Assent form (AF) according to local regulations. CYD-TDV exposed pregnant women will be actively identified and recruited using pregnancy exposures reported to the national spontaneous adverse events following immunization reporting system (SI-PNI EAPV). As such, women included in the pregnancy registry will represent those receiving care in the public and private health care settings at the time of their pregnancy exposure. The start of follow-up for the pregnant women will be the date of first CYD-TDV vaccination during the exposed pregnancy and the date of birth for the offsprings. Study outcomes will include maternal, pregnancy, birth, neonatal and infant AESIs, as well as all other reported AEs. Study data will be collected by the study investigators (or research personnel designated by the investigators) through home visit and/or telephone interviews using a structured questionnaire. Self-reported information will be supplemented and confirmed through contact with the woman's physician or other health care provider (e.g., nurse), use of medical records (e.g., prenatal care booklet, hospital, primary health care unit or other settings where antenatal care was provided), and use of record linkages with existing databases (e.g., SINASC, SIM), subject to availability. In cases of discrepancies between data sources, the medical record will be used as the gold standard for most data, followed by databases. Women will be followed for 42 days after the end of pregnancy, irrespective of the duration of the pregnancy, and their offsprings will be followed for up to 12 months post-birth.

* Exact date will depend on timing of local and national EC approvals

9.1.2 Rationale for study design

The current study is an updated version of DNG16 Version 4.0, dated 18 March 2015 originally proposed in the Risk Management Plan (RMP). The original study consisted of a multi-country, prospective Pregnancy Registry with active recruitment of pregnant women and their offspring inadvertently exposed to CYD-TDV during pregnancy (i.e., exposed cohort) identified and enrolled during an antenatal visit as early as possible during the pregnancy. It was also proposed that a similarly identified cohort of unexposed pregnant women, matched on health centre/clinic, maternal age, pregnancy trimester and estimated date of delivery (EDD), and their offsprings would serve as the comparator group (i.e., unexposed cohort). Using this approach, most of the outcomes/AEs would have been prospectively identified. The study was to be conducted in countries where CYD-TDV was first introduced, including in Latin America (Mexico, Brazil) and Southeast Asia (Philippines, Malaysia). However, a number of unexpected major barriers made the implementation of the original study design not feasible. First, there were no mass vaccination campaigns offered in Malaysia and Mexico, countries where usage was expected to be high, which was an important factor for such a rare exposure (i.e., inadvertent pregnancy exposure). Second, the targeting of children and adolescents in the Philippines (ages 9-14 years) and adolescents and young adults in Brazil (ages 15-27 in 28 of 30 municipalities offering public vaccinations campaigns) resulted in few females of childbearing age being vaccinated and even fewer inadvertently exposed during pregnancy. Finally, the short pre-notifications of pending vaccination campaigns made it impossible to plan and implement such a complex longitudinal study prior to the start of vaccination campaigns.

The non-feasibility of DNG16 as originally proposed led the MAH to re-evaluate the methodology to be used in assessing the safety of inadvertent CYD-TDV exposure

during pregnancy. As no large, public vaccination campaigns are planned in the foreseeable future outside of Brazil, the only option available was to leverage the use of existing population-based health and vital statistics databases in Brazil to identify a cohort of CYD-TDV exposed pregnant women and their offsprings, and compare the frequency/rates of adverse events among these exposed pregnancies with those of population-level estimates of these events among pregnant women of similar ages and their offsprings prior to the availability of CYD-TDV vaccination (i.e., unexposed external comparators representing background incidence).

9.2 SETTING

9.2.1 Population

The *target population* will be pregnant women of any age who received at least one dose of CYD-TDV during pregnancy or up to 30 days preceding LMP and the offsprings resulting from those pregnancies (Figure 1). The 30 day period preceding LMP is used as a conservative definition of exposed pregnancy since recall of LMP is often inaccurate; this definition has also been used in clinical trials to define an “exposed pregnancy”. When the LMP is not available, the estimated conception date (ECD) will be based on reported gestational age at ultrasound examination. The *study population* will include eligible CYD-TDV exposed pregnant women, and the offsprings from the exposed pregnancies, residing in the 30 municipalities of Paraná (Brazil) where public vaccination campaigns have taken place at the time of their pregnancy exposure who provide signed informed consent. These women will be actively identified using the SI-PNI-AEPV database and will, therefore, represent women receiving care in the private and public health care sectors.

[figure not shown]

Figure 1. Assessment of CYD-TDV inadvertent pregnancy exposure status

The study could be extended to other regions and States of Brazil provided that: (i) large scale immunization campaigns including women of childbearing age take place, (ii) sufficient notification of such campaigns is received to permit the implementation of this PASS, (iii) individual-level immunization registries are available and linkable

to other data sources, (iv) Ministry of Health (MoH) and Departments of Health (DoHs) are willing to collaborate and provide investigators access to the necessary data and databases, and (v) approval is obtained from the relevant Ethics Committee(s) in accordance with local regulations.

9.2.2 Participant recruitment and follow up

CYD-TDV exposed pregnant women of any age will be actively identified and recruited using the SI-PNI EAPV database. As soon as the study has received Ethics approval from the relevant committees, Paraná's Secretary of Health (Secretaria do Estado da Saúde do Paraná) will extract the list of exposed pregnant women captured in the EAPV database up to that time point; this will assist with study planning as investigators will receive the distribution of potential study participants by municipality/city at the start of the study. This information will be copied to an encrypted and password protected USB pen drive and delivered to the study's Principal Investigator (PI). The exposed pregnant women's nominal data (name, phone number, address, and email) will be extracted from the SI-PNI EAPV database to enable Study Investigators or the research personnel designated by the investigators (hereafter referred to as their "delegate[s]") to contact them or their legal representative if a minor, to describe the study and arrange to obtain the signed ICF/AF from those who agree to participate. The study investigators will be the only persons with access to nominal data. Three attempts will be made to contact potential study participants before considering her "unreachable".

Since the implementation of Paraná's dengue immunization programs will precede the study's start of participant enrollment date follow-up and data collection will be retrospective for a large proportion of study participants. However, pregnant women inadvertently exposed to CYD-TDV during vaccinations campaigns implemented either within a few months before or after the start of enrollment will be followed prospectively. For prospectively enrolled women, designated personnel at Paraná's Secretary of Health will query the SI-PNI EAPV database on a bi-monthly basis to identify newly exposed pregnant women. Depending on data availability, the periodicity may be modified.

Participants' date of CYD-TDV immunization will be confirmed through probabilistic linkage (i.e., using nominal data) with the immunization registry; database linkages will be carried out by the DoH or study investigators depending on the availability of qualified personnel. When indicated, a women's self-reported exposure status will be reclassified using the immunization registry as the gold standard. In addition, reports of multiple CYD-TDV exposures during a pregnancy will be classified according to the earliest pregnancy exposure.

Women enrolled in the CYD-TDV pregnancy registry will be followed from the date of their first CYD-TDV vaccination during pregnancy (cohort entry) to up to 42 days following the end of the exposed pregnancy, regardless of the outcome of the pregnancy. The offspring of the exposed pregnancy will be followed for up to 12 months post-birth. In addition, women and offsprings enrolled prospectively (i.e., CYD-TDV exposure either soon before or after study start) will be followed until the earliest of: date of lost to follow-up, withdrawal of consent or death or end of study (July 2022).

9.2.3 Selection of a comparison group

This pregnancy registry study will be a combination of a retrospective (outcomes occurred before the start of participant enrollment) and prospective (outcomes occurred after the start of participant enrollment) cohort study using active identification and enrollment of pregnant women and their offsprings inadvertently exposed to CYD-TDV during pregnancy or up to 30 days preceding the LMP. For reasons described in section 9.1.2, active enrollment of a valid internal comparison group of unexposed pregnant women and their offsprings is not feasible. As such, rates of study AESIs observed among women enrolled in the pregnancy registry and their offsprings will be compared with available background event rates prior to the availability of CYD-TDV for the Brazilian population of similarly aged women and offsprings (i.e., external unexposed comparators) to identify potential safety signals warranting further investigation. Background rates from existing databases (e.g., SISPRENATAL, SINASC, SIM) and other appropriate data sources (e.g., literature) will be used.

9.2.4 Study period

The study pregnancy registry will capture CYD-TDV pregnancy exposures from July 2016 to July 2020 for women (or their legal guardian/representative if a minor) who consent to participate. As such, study outcomes will be retrospective from July 2016 to the start of participant enrollment and prospective if occurring after the start of participant enrollment. The exact start date for participant enrollment will depend on the timing of local and national EC approval but is anticipated for July/August 2019 (to be confirmed).

The study start date of July 2016 corresponds to the start of availability of Paraná's immunization registry and the availability of CYD-TDV through the private sector, while the participant enrollment end date of July 2020 will permit the inclusion of some prospectively followed women and their offsprings *provided* large public vaccination campaigns continue to be offered in Paraná or in other States of Brazil after the start of the study's enrollment period. As previously mentioned, the study could be expanded to other regions of Brazil *provided* the feasibility criteria listed in section 9.2.1 are fulfilled.

9.2.5 Eligibility criteria

9.2.5.1 Inclusion criteria

- CYD-TDV exposed pregnant women of any age residing in the 30 municipalities of Paraná where public vaccination campaigns have been offered at the time of their pregnancy exposure, and whose pregnancy exposure was reported to Brazil's AEFI PV database (SI-PNI AEPV);
- Valid contact information (in SI-PNI AEPV);
- Study participants must provide a signed and dated informed consent form (ICF) or assent form (AF) (based on local regulations), and/or a signed and dated ICF by the parent(s) or other legally acceptable representative (and by an independent witness if required by local regulations) if a minor.*

* Women who meet the inclusion criteria and provide informed consent to participate and complete the structured interview, but who do not consent to medical record review and/or database linkages will still be included in the study; however, their data will be analyzed separately in a sensitivity analysis.

9.2.5.2 **Exclusion criteria**

- Presence of a major language barrier, medical or psychiatric condition that would prevent a woman from providing informed consent or accurate medical or medication/vaccination histories.

9.2.6 **Investigator selection**

The study investigators were selected on the basis of their expertise in pediatrics, maternal and child health, epidemiology and clinical research, as well as their expertise with Brazil's public and health databases and their access to these databases (Appendix 1). In addition, these investigators were recommended by Paraná's Secretary of Health.

9.3 **VARIABLES**

9.3.1 **Primary endpoints**

The primary study endpoints will include all serious and non-serious maternal, pregnancy related, birth outcomes, neonatal and infant events as described below occurring anytime between cohort entry and the end of follow-up for each event. Although formal diagnostic criteria such as those of the Brighton Collaboration are available for a number of the outcomes of special interest, it is unlikely that these are used in routine clinical practice. As such, the diagnoses will be based on clinician assessment as recorded in the medical record and/or databases.

- **Maternal adverse events following immunization:** will be defined as all reported adverse events following immunization (serious and non-serious) occurring *independent of the pregnancy* (e.g., injection site reactions, systemic reactions).
- **Pregnancy related events:** will be defined as study AESIs (see Appendix 2) and other reported adverse events (serious and non-serious) occurring during the pregnancy, labour and delivery, or the puerperium. Pregnancy related AEs will be classified as: (i) pregnancy outcomes, (ii) complications of pregnancy, and (iii) complications of labour, delivery and puerperium. These outcomes were chosen based on their frequent presentation, their importance as markers of maternal and/or infant health, and their public health relevance. In addition, chorioamnionitis and hypertensive disorders of pregnancy are major risk factors for preterm birth. The definitions used for these outcomes will be consistent with local clinical practice, the European Medicine Agency (EMA) and United States Federal Drug Agency (US FDA) pregnancy guidance documents, and other published pregnancy outcome classification systems such as the European Surveillance of Congenital Anomalies (EUROCAT).
- **Birth outcomes:** will be defined as study AESIs and other reported adverse events (serious and non-serious) observed or diagnosed at birth. See Appendix 3 for the list of birth outcomes of special interest and their definition.
- **Neonatal and infant events:** Neonatal events will be defined as study AESIs and other reported adverse events (serious and non-serious) occurring between the day of birth (DOB) and 28 days post-DOB. Study AESIs and other reported adverse events (serious and non-serious) occurring between day 29 and 365 post-birth will be classified as infant events. See Appendix 4 for the list of neonatal and infant events of special interest and their definition.

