- (v) *Paraná State Immunization registry*: This state-level database captures information on CYD-TDV vaccinations administered during public vaccination campaigns. CNS numbers are not systematically recorded in the registry; hence, data will be retrieved using probabilistic linkage. This database will be used to confirm the dates of CYD-TDV vaccination.

The DoH of Paraná administers this database and it is possible to have access to all data for a specific study following a specific request and approval from the appropriate local ethics committee. Data access is requested via the State Department of Health of Paraná.

- (vi) *SINASC*: Brazil's national live birth registry database. This database includes information on some maternal risk factors, delivery conditions, baby's condition at birth and presence of malformations. SINASC will be used to supplement and verify self-reported delivery, birth and neonatal outcomes, and to provide population-level AE background rates (i.e., external unvaccinated comparator data) for the safety analysis.

In Brazil, SINACS is administered by the MoH and it is possible to have access to all data for a specific study following a specific request and approval from the appropriate local ethics committee. Data access may be requested via the State Department of Health of Paraná.

- (vii) *SIM*: Brazil's national mortality database. This database captures information on causes of death, as well as maternal and infant demographics. It will be used to supplement and verify maternal, neonatal and infant deaths.

In Brazil, SIM is administered by the MoH and it is possible to have access to all data for a specific study following a specific request and approval from the appropriate local ethics committee. Data access may be requested via the State DoH of Paraná.

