9.7.4 Sensitivity analyses

The following sensitivity analyses will be undertaken to test the robustness of the results:

- The primary analysis will be repeated restricted to women receiving care from the public health care sector only as SIPNI/EAPV includes women from both the private and public sector but outcome data for women receiving care in the private sector will be limited to those that are self-reported as the available health and mortality databases reflect care provided in the public sector and the medical records of women in the private sector may not be accessible. Women receiving care from both sectors will be classified as having a private coverage.
- To address the possibility of bias owing to the retrospective nature of some outcomes data, the analysis will be repeated stratified by the nature of the outcomes (i.e., prospective vs. retrospective).
- To address the possibility of misclassification of exposure due to the use of a “30 days prior to the LMP” conservative criteria for the definition of “exposed pregnancy,” the analysis will be repeated excluding pregnancies and offsprings exposed during the preconception period (LMP - 30days) if available data permits.
- To address potential bias introduced by study participants who did not consent to medical chart review and/or database linkages, the analyses will be repeated by excluding these study participants.

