9.9 STRENGTHS AND LIMITATIONS OF THE RESEARCH METHODS

The most important strength of this study is that, unlike most pregnancy registries that rely on passive reporting, the identification and enrollment of pregnancy exposures will be active. Another important strength is that self-reported vaccination status and outcomes will be verified using medical record review and database linkages; thereby mitigating the risk of recall and reporting bias, a potential danger with retrospectively collected outcomes. Also, offsprings will be followed for up to 12 months post-birth to assess the risk of birth defects that may not be detected at birth, and to assess the risk of hospitalized and/or severe dengue among infants exposed in utero. On the other hand, this study will also have some limitations that need to be considered. First, the baseline dengue serostatus of most exposed pregnant women will not be known as the vaccinations studied occurred before the recent "test and vaccinate" recommendation. As such, should a safety concern arise, it will not be possible to distinguish between vaccine associated dengue in seronegative vaccinees from vaccine failure or waning immunity in seropositive vaccinees. Second, the majority of outcomes will be ascertained retrospectively, thus increasing the risk of recall and detection bias. However, this risk will be, in part, mitigated by the identification of outcomes using multiple data sources, and by the use of a sensitivity analysis stratified according to the nature of the outcomes (i.e., prospective vs. retrospective) if a sufficient number of women can be prospectively enrolled. Third, women who are unreachable, refuse to participate or have died prior to enrollment may be systematically different from study participants and thus, could introduce bias. However, permission will be sought from the Ethics Committee to obtain *aggregate* level information to undertake a comparison of participants and non-participants with regards to baseline characteristics and characteristics of prenatal care to assess the likelihood, strength and direction of such bias. Fourth, although the identification of CYD-TDV exposed pregnant women will be active, the database used to identify these women (SI-PNI EAPV) is part of Brazil's passive AEFI reporting system. As such, some pregnancy exposures may be missed despite educational efforts to stimulate reporting; however, there is no reason to believe that pregnancy exposures captured in the database will be systematically different from those who may be missed. As such, this will impact the precision of the results but not their validity. Fifth, the use of multiple data sources for identifying outcomes may introduce some discordance; however, the impact of this on outcome misclassification will be minimized by choosing *a priori* a gold standard source for each event. Sixth, given the young age of most vaccinees in Paraná, it is possible that many of the pregnancy exposure will be in adolescents; an age group less likely to carry the pregnancy to

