APPENDIX 2. PREGNANCY RELATED ADVERSE EVENTS OF SPECIAL INTEREST

Outcome	Description
Pregnancy outcomes	
Ectopic pregnancy	
 • Pregnancy with fertilized egg implanted and maturing outside the uterus; • Based on clinician assessment as recorded in the medical record or databases
Pregnancy loss	
Spontaneous abortion/miscarriage	
 • Fetal death with expulsion at <20 weeks of gestation or at weight <500 g if gestational age is unknown; occurred naturally (without outside interference); • Based on clinician assessment as recorded in the medical record or databases
Abortion, unspecified	
 • Premature expulsion of the embryo or a non-viable fetus where the type of abortion (spontaneous or elective) is not mentioned; • Based on clinician assessment as recorded in the medical record or databases
Abortion, medically indicated	
 • Abortion brought on intentionally; includes therapeutic abortion when pregnancy is a threat to the mother's life and/or is the result of sexual assault; • Based on clinician assessment as recorded in the medical record or databases
Termination of pregnancy for fetal anomaly (TOPFA)	
 • Abortion brought on intentionally when the embryo/fetus presents an abnormality
Stillbirth/fetal death	
 • Delivery of a dead fetus at ≥20 weeks of gestation or in fetus weighing >500 grams if gestational age is unknown; • Based on clinician assessment as recorded in the medical record or databases
Death in utero	
 • Fetal death without expulsion at < 20 weeks of gestation; • Based on clinician assessment as recorded in the medical record or databases
Complications of pregnancy	
Hypertensive disorders	All with onset at ≥20 weeks gestation
Gestational hypertension	
 • Hypertension (sustained blood pressure ≥140/90 mmHg) that develops during pregnancy in previously normotensive woman; • Based on clinician assessment as recorded in the medical record or databases
Preeclampsia	
 • Gestational hypertension with proteinuria (>300mg in 24 hrs); • Based on clinician assessment as recorded in the medical record or databases

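### Losses are defined by a clinician's record, but the protocol also relies on self-report alone for some women, so a loss known only from the woman has no settled status

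*Protocol*

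**What the plan says.** Section 9.3.1 (Primary endpoints) explains that formal diagnostic criteria are unlikely to be used in routine practice, and concludes that "the diagnoses will be based on clinician assessment as recorded in the medical record and/or databases". In Appendix 2, spontaneous abortion is "Fetal death with expulsion at <20 weeks of gestation or at weight <500 g if gestational age is unknown", occurring naturally, and the row adds: "Based on clinician assessment as recorded in the medical record or databases".

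On conflicting sources, section 9.1.1 says: "In cases of discrepancies between data sources, the medical record will be used as the gold standard for most data, followed by databases". Section 9.9 promises that "a gold standard source for each event" will be chosen in advance, but the protocol gives no list by event.

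Other sections treat the woman's own report as an outcome source:

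- Section 9.4 lists the structured questionnaire as a primary data source that ascertains pregnancy outcomes. Medical records supplement and verify it.
- Section 9.7.4 says that "outcome data for women receiving care in the private sector will be limited to those that are self-reported".
- Section 9.2.5.1 keeps women who complete the interview but refuse record review or linkage, and 9.7.4 removes them only in a sensitivity analysis.

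Of the linked databases in 9.4, SINASC is "Brazil's national live birth registry database". SIM is to verify maternal, neonatal and infant deaths. SISPRENATAL covers public-sector antenatal and puerperium visits and is assigned to verify pregnancy related outcomes.

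**The concern.** The protocol sets one case definition for a loss and then includes women who cannot meet it. A woman may report a miscarriage that no accessible record shows, because it never reached care, because her care was private, or because she refused record review. The protocol does not say whether her pregnancy is then an event, a non-event or an unknown outcome. Two analysts could classify it differently, and each could cite a section in support.

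Spontaneous abortion is the most frequent outcome in the precision calculation of section 9.5, and the one measured with the best relative precision. Sections 9.2.3 and 9.7.1 compare observed rates with background rates to look for safety signals. If losses in exposed women need a clinician's entry and the background rate does not, the comparison leans towards finding no signal.

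**Working it through.** **The definition against the sources**

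1. Where Appendix 2 intends alternative criteria, it can say so: the eclampsia and postpartum-haemorrhage rows join theirs with 'or'. The spontaneous-abortion row has no such link, so its natural reading is that a clinician's entry is needed.
2. Section 9.7.4 repeats the primary analysis in public-sector women only. Private-sector women are therefore in the primary analysis, with self-reported outcomes. Under the definition in step 1 their losses could not qualify.
3. Section 9.7.4 also repeats the analyses without women who refused chart review or linkage, so they too are in the main analysis.
4. Neither sensitivity analysis reaches a consenting public-sector woman whose loss nobody recorded.
5. No listed database is described as recording early losses. SISPRENATAL comes closest, but no loss field is mentioned, and section 9.8.1 says its visits after the first are less complete than those in the prenatal booklet.

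**The plan's own figure**

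Section 9.5 takes a risk of 1/7 and 214 reported exposures. 214/7 = 30.6, rounded to 31 losses; 31/214 = 14.486%. The exact (Clopper-Pearson) 95% interval is 10.06% to 19.93%, as stated.

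**Size if self-report-only losses are not counted**

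Let u be the share of losses with no accessible record. The documents do not give u; 10%, 25% and 40% are assumptions for illustration. The true risk is p = 1/7.

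- Kept as non-events: observed risk = p(1 − u).
- Dropped as unknown, using the known-outcome denominator of 9.7.1: observed risk = p(1 − u)/(1 − pu) = (1 − u)/(7 − u).

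The masked relative risk is the true excess over 1/7 that would still be observed as 1/7:

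- Non-events: p(1 − u) = 1/7 gives a relative risk of 1/(1 − u).
- Dropped: p(1 − u)/(1 − pu) = 1/7 gives p = 1/(7 − 6u), so a relative risk of 7/(7 − 6u).

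| u (assumed) | Observed, non-events | Masked RR | Observed, dropped | Masked RR |
|---|---|---|---|---|
| 10% | 0.90/7 = 12.9% | 1/0.90 = 1.11 | 0.90/6.90 = 13.0% | 7/6.4 = 1.09 |
| 25% | 0.75/7 = 10.7% | 1/0.75 = 1.33 | 0.75/6.75 = 11.1% | 7/5.5 = 1.27 |
| 40% | 0.60/7 = 8.6% | 1/0.60 = 1.67 | 0.60/6.60 = 9.1% | 7/4.6 = 1.52 |

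In whole counts at 214 pregnancies, missing 9 of 31 losses (about 30%) gives 22/214 = 10.3% or 22/205 = 10.7%, still inside the planned interval. Missing 16 of 31 (about half) gives 15/214 = 7.0% or 15/198 = 7.6%, below its lower limit.

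**The case against.** The strongest reply is that the protocol never says a self-reported loss is discarded. The sentence in 9.3.1 explains why routine clinical diagnosis replaces formal criteria such as those of the Brighton Collaboration; it need not be a rule for excluding unverified reports. The endpoints also take in other reported adverse events. The ranking in 9.1.1 applies only to discrepancies and to most data. Section 9.9 promises a gold standard for each event, and that list could properly sit in a statistical analysis plan that is not at hand.

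Much of this stands, and it rules out three stronger readings that a reader might infer:

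- **That self-report can never prevail.** It is absent from the stated ranking, but the ranking is limited as above, and 9.7.4 accepts self-report as the only source for private-sector women.
- **That no listed database holds miscarriages.** The protocol is silent on the loss content of SISPRENATAL. Hospital records, primary-care records and the prenatal booklet are sources too.
- **That the loss rate is biased below background.** Section 9.2.3 allows background from databases or literature and fixes no source for miscarriage. If the background is record-based, counting self-report-only losses in exposed women alone would push the comparison upwards. Section 9.8.1 also names closer attention and follow-up that could detect more events.

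What the reply does not remove is the conflict. The record-based definition appears in both 9.3.1 and Appendix 2, and the women it cannot serve are in the primary analysis. A promised gold standard does not say whether a silent record counts as disagreement.

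**Conclusion.** The definition of a loss in 9.3.1 and Appendix 2 conflicts with the use of self-report in 9.4 and 9.7.4 and with the women retained under 9.2.5.1. The status of a loss known only from the woman is unresolved. If the definition is applied as written, the observed loss risk falls under either denominator rule. The fall runs from about 1 percentage point at an assumed 10% unrecorded to between 5 and 6 points at an assumed 40% (14.3% to 9.1% or 8.6%). The actual unrecorded share, and so the actual size, is unknown. A bias against background follows only if the background rate includes losses without a clinician's record. The point deserves correction because the outcome is the most frequent one planned and the remedy is cheap; it does not show that the study's result will be wrong.

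**What to change.** Reconcile 9.3.1, Appendix 2, 9.4 and 9.7.4:

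- State that a self-reported loss counts as an event unless a record or a linked birth contradicts it.
- Flag each loss in the eCRF as record-confirmed or self-report only.
- Add to 9.1.1 that a silent record is not a discrepancy. Its ranking already applies only where sources differ, so this is a clarification.
- Report the loss risk twice: for all losses and for record-confirmed losses only.
- Where the background rate is record-based, make the comparison with the confirmed-only figure, so that both sides are ascertained alike.

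The cost is protocol wording, one data field and one extra table. The downside is that some self-reported losses may be wrong; the confirmed-only figure shows how much they matter.
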